6.2 Randomisation

Not applicable.

6.3 Interim Analysis

Not applicable.

7 STATISTICAL ANALYSIS

7.1 General

Smith+Nephew's Global Biostatistics group will conduct the statistical analysis for this study. Unless otherwise stated, significance tests and hypothesis testing will be two-sided, performed at the 5% significance level. Resulting p-values will be quoted and 95% two-sided confidence intervals will be generated where appropriate. All p-values will be rounded to three decimal places, p-values less than 0.001 will be presented as '<0.001' in all tables.

CONFIDENTIAL AND PROPRIETARY

This document contains information that is confidential and proprietary to Smith & Nephew PLC and Smith & Nephew, Inc. and is intended for use only by Smith+Nephew and its manufacturer. It shall not be reproduced or copied in whole or in part, nor shall the contents be disclosed by any means without prior written permission from Smith+Nephew, nor shall anyone make any use of it that is contrary to the expressed or implied wishes of Smith+Nephew.

Statistical Analysis Plan

A Prospective, Multi-Center, Non-Randomized, Safety and Efficacy Clinical Study of the LEGION™ Primary Knee System for Primary Total Knee Replacement in Subjects with Degenerative Knee Disease

Number: 10-4042
ST: 1113
Version: Final 1.0, 15-Feb-2021
Page: 9 of 18

Where data summaries are specified, categorical and ordinal variables will be summarized with frequencies and percentages. Continuous variables will be summarized with the following summary statistics: number of observations, mean, median, standard deviation, minimum and maximum values.

7.2 Analysis Populations

The "Safety" population (SAF) will be used as the analysis population for summarizing all data. This is defined as all knees (or subjects) enrolled into the study and who were implanted with the study device.

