3. Subject has an active localized or systemic infection;
4. Subject is pregnant;
5. Subject psychological or neurological conditions that would impair the subject's ability or willingness to restrict activities or follow medical advice during the course of this study;
6. Subject is a prisoner.

VI. STUDY PROCEDURES

A. Prior to Study Initiation

The following documents must be provided to Smith & Nephew prior to study initiation:

1. Copies of the IRB approval letter and IRB approved informed consent for each institution used by the Investigator for the clinical study.
2. A signed Statement of Investigator.
3. A current, signed, dated CV and medical license for the Principal Investigator documenting the location where the study will be conducted.

B. Subject Enrollment

1. Screen Subject – All subjects who present with total knee osteoarthritis requiring joint replacement will be screened for eligibility in the study based on physical exam and radiographic evaluation of the joint.
2. Informed Consent – If the subject meets all inclusion and exclusion criteria, a consent form is presented to the subject. If the subject elects to participate in the study, the subject must sign the consent form prior to completing any study related activities.
3. Preoperative Evaluation – After the subject meets the entrance criteria and signs the consent form, the appropriate preoperative study activities are to be completed.

C. Operative Procedures

1. Surgical Technique

The medical device will be implanted using standard surgical technique(s), depending on the individual investigator's standard procedure. Instrumentation specific for the device will be used. A surgical technique brochure for implanting the LEGION® Total Knee System will be provided to each investigator.

2. Operative Data

Operative data and device information will be collected. All operative adverse events will also be reported.

D. Postoperative Procedures

Adverse events occurring during the hospital stay will be reported. Discharge information will also be captured.

E. Follow-up Procedures

Subjects will be evaluated clinically at 3 months, 1 year, 2 years, 3 years, 5 years, 7 years, and 10 years postoperative. Please see Section I, "Schedule of Events" Table for details and visit windows.

All radiographic observations are to be reported on the radiographic form. Postoperative device-related and surgical adverse events are to be reported.

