For the current study, the revision free rate will be based on knowledge of parametric proportional hazards models. The survival times with an exponential distribution have a constant hazard function associated with exponential distributed survival time. Thus, for individuals sampled from this exponential survival distribution, the probability of surviving beyond time $t=8$ years is 0.95. The entire survival distribution can be defined by the same parameter value $\lambda=0.0064$ (nQuery Advisor 6.01).

B. Non-inferiority Analysis

As previously reported, an annual survival rate was extrapolated using equivalency of exponentially distributed survival times to determine 10 year survivorship. As such, the current 10-year investigation will utilize a control survival rate of approximately 93.7% (nQuery Advisor 6.01).

All subjects implanted with the LEGION® Primary Knee System, who meet the inclusion and exclusion criteria and who gave their voluntary consent to participate in the study will be included in the analysis. The analysis will include the description of subject demographics and baseline characteristics. Accountability data will include the number of subjects enrolled and the followup data collected. Data will be analyzed separately for changes from preoperative at 3 months, 1 year, 2 years, 3 years, 5 years, 7 years, and 10 years(if required). Safety will be assessed by identifying and summarizing device-related adverse events throughout the study.

The sample size is calculated based on the non-inferiority of the study device; the following hypotheses will be tested to test the difference in cumulative percent survival of the study device with the literature reference rate with a non-inferiority margin, $\delta>0$:

$$H_0: \pi_0 - \pi \geq \delta$$

$$H_a: \pi_0 - \pi < \delta$$

Where π is the cumulative percent survival of study device and π_0 is the reference rate, respectively. $\delta=0.07$. For these hypotheses, rejection of the null hypotheses will imply non-inferiority of the study device compared to the reference rate.

For the above hypotheses, the sample size for a specified α and power $100(1 - \beta)\%$ is given by,

$$n = \frac{(z_\alpha + z_\beta)^2 [\pi (1 - \pi)]}{(\pi_0 - \pi - \delta)^2}$$

(Chow et al, 2003), where δ is the non-inferiority margin and nonnegative number.

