7.6 Disposition Data

The disposition of subjects (knees) will be summarized as using accountability of clinical follow-up of the subjects' knee from the preoperative, operative through the 10 year postoperative follow-up. Information that will be summarized in this table will include but not only restricted to theoretically due, revisions, terminations, expected knees at visit, not yet overdue at visit and knees evaluated at visit.

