7.11 Analysis of Secondary Endpoints

- Surgical and device-related AEs will be summarized using numbers (n) and percentages. The count of episodes for each of these events will also be presented.
- All KSS and KOOS scores will be summarized by visit (preoperative to 10 years) using descriptive statistics for continuous variables. Changes from preoperative to all postoperative visits will additionally be summarized (except for KSS expectation).
- For radiographic evaluations, the proportion of knees with evaluations performed will be summarized. Of those knees with radiographic evaluations performed the proportion of knees with radiolucent lines observed within the femoral zone, tibial ML zone, tibial AP zone and the patellar zone will be summarized. Additionally among knees with radiolucent lines, the number of zones with radiolucent lines present will be summarized using descriptive summary characteristics for continuous variables. The cumulative sum of radiolucent lines will also be summarized using descriptive statistics for continuous variables.
- The proportion of knees evaluated with periosteal hypertrophy, implant loosening, osteolysis or subsidence will be summarized.
- The proportion of knees with patellar problems such as dislocation, abnormal placement or subluxation will be summarized.

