7.13 Analysis of Safety Endpoints

- An overall summary AE table that would summarize as number (n) and percentages (%), the overall incidence according to knees with at least one AE; knees with an AE by worst

CONFIDENTIAL AND PROPRIETARY

This document contains information that is confidential and proprietary to Smith & Nephew PLC and Smith & Nephew, Inc. and is intended for use only by Smith+Nephew and its manufacturer. It shall not be reproduced or copied in whole or in part, nor shall the contents be disclosed by any means without prior written permission from Smith+Nephew, nor shall anyone make any use of it that is contrary to the expressed or implied wishes of Smith+Nephew.

Statistical Analysis Plan

A Prospective, Multi-Center, Non-Randomized, Safety and Efficacy Clinical Study of the LEGION™ Primary Knee System for Primary Total Knee Replacement in Subjects with Degenerative Knee Disease

Number: 10-4042
ST: 1113
Version: Final 1.0, 15-Feb-2021
Page: 17 of 18

relationship to study device; knees with at least one AE with an involvement with a study knee; knees with at least one AE by worst severity (mild, moderate, or severe); knees with at least one AE by worst outcome and; knees with any AE that led to discontinuation from study.

- Other events that will be summarized within the overall summary AE table include SAEs, ADEs, SADEs, UADEs and USADEs. These tables will also include the cumulative episodes of events encountered.
- ISO tables will be summarized as appropriate.
- An AE listing will be provided which would display these AE characteristics by study knee as well as systemic AEs.

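### The SAP's only analysis set requires that the device was implanted, so operative adverse events in operated but unimplanted knees fall outside the AE tables

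*SAP*

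**What the plan says.** SAP 7.2 names a single population, called Safety, which "will be used as the analysis population for summarizing all data". Membership has two conditions: "all knees (or subjects) enrolled into the study and who were implanted with the study device". The SAP defines no enrolled set and no surgery-started set.

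The adverse event sections name no other denominator. SAP 7.11, on the secondary endpoints, says "Surgical and device-related AEs will be summarized using numbers (n) and percentages", and SAP 7.13 builds its overall AE table on counts of knees. By 7.2, both use implanted knees. SAP 7.13 also plans a listing: "An AE listing will be provided which would display these AE characteristics by study knee as well as systemic AEs". No population is named for it.

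The protocol's reporting rule carries no such condition. Under Operative Data in VI.C it says "All operative adverse events will also be reported". Its analysis set does carry one: VIII.B covers "All subjects implanted with the LEGION® Primary Knee System, who meet the inclusion and exclusion criteria" who also consented. The same paragraph of VIII.B adds "Accountability data will include the number of subjects enrolled and the followup data collected". SAP 7.6 plans disposition as "accountability of clinical follow-up of the subjects' knee from the preoperative, operative through the 10 year postoperative follow-up", and says its contents are not confined to the items it names.

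**The concern.** Enrolment and implantation are separate events in this study. Protocol VI.B places screening, consent and the preoperative evaluation before surgery, and SAP 7.2 itself lists enrolment and implantation as two conditions. Between them lies the operation, and a subject can enter it without leaving with the study device.

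An operative adverse event in such a subject is to be reported under protocol VI.C, and the schedule of events provides an adverse event form at the operative/discharge visit. It would be an event of the kind the secondary endpoint covers (protocol IV; SAP 5.2). It would still be absent from the tables that summarise that endpoint, because membership of the Safety population depends on the outcome of the surgery. Operations that did not go as planned are the ones removed, and these may well be more likely than others to carry a surgical event.

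The stake is the accuracy of a descriptive rate. SAP 7.15 drops the non-inferiority test, so counts, percentages and survival estimates are what the study will deliver, and their denominators should be right.

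**Working it through.** **Which rule governs which output**

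| Output | Population named in its own section | Population by SAP 7.2 | Operated but unimplanted knee |
|---|---|---|---|
| Surgical and device-related AE table (SAP 7.11) | none | implanted | excluded |
| Overall AE table (SAP 7.13) | none | implanted | excluded |
| AE listing (SAP 7.13) | none | implanted, if 7.2 covers listings | not assured |
| Disposition (SAP 7.6) | none, but starts preoperatively | implanted, if read literally | unclear |
| Survivorship, KSS, KOOS, radiographs | none | implanted | properly excluded |

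The first two rows follow directly from 7.2. The disposition row is a conflict between two sections: a table that starts before surgery can show subjects who were never implanted, but applying 7.2 to all data would remove them. The rows named in 7.6 include neither enrolled nor not implanted.

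**Size**

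The plan gives no figure for this point. The only plan number used is the enrolment target of 138, which follows from 96 evaluable subjects and 30% loss: 96 / 0.70 = 137.1, rounded up to 138. Everything else is assumed.

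Let N be the operated knees, k those operated but not implanted, x the implanted knees with a surgical AE, and e the unimplanted knees with one.

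- Rate under SAP 7.2: x / (N − k)
- Rate among all operated: (x + e) / N

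Take N = 138, that is, every enrolled subject operated on one knee. First set e = k, so that every unimplanted case has an event. This is the worst case.

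| x | k | e | SAP 7.2 | All operated |
|---|---|---|---|---|
| 7 | 0 | 0 | 7/138 = 5.1% | 7/138 = 5.1% |
| 7 | 1 | 1 | 7/137 = 5.1% | 8/138 = 5.8% |
| 7 | 3 | 3 | 7/135 = 5.2% | 10/138 = 7.2% |
| 7 | 5 | 5 | 7/133 = 5.3% | 12/138 = 8.7% |
| 10 | 1 | 1 | 10/137 = 7.3% | 11/138 = 8.0% |
| 10 | 3 | 3 | 10/135 = 7.4% | 13/138 = 9.4% |
| 10 | 7 | 7 | 10/131 = 7.6% | 17/138 = 12.3% |

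The assumption e = k drives the gap. With x = 7 and k = 3, a single event among the three gives 8/138 = 5.8% against 5.2%. With no event among them it gives 7/138 = 5.1% against 5.2%, so the bias vanishes and reverses very slightly. In general the rate is understated when e/k exceeds x/(N − k). The count of knees with an event is understated whenever e is at least 1.

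**The case against.** Several points on the other side are sound.

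- **No undeclared change.** A reader might infer that the SAP narrowed the population and that 7.15 should have said so. It did not. Protocol VIII.B already limits the analysis to implanted subjects, and SAP 7.2 is if anything wider, since it omits the protocol's eligibility condition.
- **The enrolment count is not shown to be lost.** A reader might also infer that the number enrolled disappears from every table and that selection between consent and surgery is hidden. Protocol VIII.B requires that number, SAP 7.15 withdraws only the non-inferiority test, and SAP 7.6 starts preoperatively with open-ended contents. What stands is narrower: the reference to all data in 7.2 is not reconciled with the enrolment accountability in VIII.B, and 7.6 does not name the row.
- **Listings may still show such events.** The AE listing in SAP 7.13 and the deviation listing in SAP 7.7 name no population. That is fair, but 7.2 does not assure inclusion, and a listing supplies no rate.
- **Protocol VI.C may be only a duty on sites.** The sentence sits with operative data collection and fixes no table denominator. This weakens any claim of outright contradiction. It does not explain why events collected for a secondary endpoint should be left out of its summary.
- **The case is hypothetical.** Neither document mentions an abandoned implantation, and subjects must be candidates for the device under its instructions for use. The number may be zero. The definition should nevertheless not depend on that.
- **No decision turns on it.** Surgical AEs are summarised without a test and the primary endpoint is now descriptive. This limits the importance of the point but does not remove it.

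**Conclusion.** The point holds in a limited form. Read literally, SAP 7.2 leaves operative adverse events in operated but unimplanted knees outside the tables of SAP 7.11 and 7.13. This is a stated rule, not a matter left open.

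The size is unknown. It is zero if there were no such cases. If there were one to five, each with an event, and 7 implanted knees had a surgical AE among 138 operated, the reported rate would be about 0.7 to 3.4 percentage points too low (5.8 − 5.1; 8.7 − 5.3). These figures rest on assumed counts, on one knee per subject, and on an event in every unimplanted case, so they are an upper illustration and not an estimate.

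Survivorship, scores and radiographs are unaffected, because an implanted set is right for them. On enrolment, the documents support only a request to reconcile SAP 7.2 and 7.6 with protocol VIII.B.

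**What to change.** Amend SAP 7.2 and 7.6 as follows.

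1. Define the Safety set, for all AE summaries in 7.11 and 7.13, as every knee of an enrolled subject in which the study surgery was started. Report the number of subjects beside the number of knees, because SAP 7.5 allows for bilateral cases.
2. Keep the present definition under its own name, as an implanted set, for Kaplan-Meier survivorship, KSS, KOOS and radiographs.
3. State that the 7.6 disposition table starts from all enrolled subjects, with rows for not operated and for operated but not implanted.
4. State that the AE listing follows the new Safety set.

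The cost is SAP wording and a few rows in the table shells. The operative/discharge and adverse event forms already exist, but their contents are not shown, so whether the reason for non-implantation is captured needs checking. The surgical AE rate may become slightly less favourable. If no such case occurred, a zero in the disposition table shows it and the AE rates are unchanged.

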7.3 Handling of Missing, Incomplete and Repeat Data

Missing value imputation would be carried out on KSS endpoints. According to instructions for the derivation of the KSS endpoints, in an event that there are fewer than 50% missing responses within a domain, imputation with values equal to the average of all of the other items in the same domain would be used (KSS User Manual, 2012).

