7.4 Derived Data

Age

- Age (in years) = INT{(Operative Date)-(Date of Birth)+ 1/365.25}

Body Mass Index (BMI)

- BMI = {(Weight in kg)/(Height in m)²}, if units are in kg for weight and m for height OR;
- BMI = {(Weight in lbs)x703.07})/(Height in inches)²}, if units are in lbs for weight and inches for height (Adjustments made to formula to standardize BMI unit to kg/m²)

Time to Revision

- Time to revision (in months) = (Revision Date – Operative Date + 1)/30.4375

CONFIDENTIAL AND PROPRIETARY

This document contains information that is confidential and proprietary to Smith & Nephew PLC and Smith & Nephew, Inc. and is intended for use only by Smith+Nephew and its manufacturer. It shall not be reproduced or copied in whole or in part, nor shall the contents be disclosed by any means without prior written permission from Smith+Nephew, nor shall anyone make any use of it that is contrary to the expressed or implied wishes of Smith+Nephew.

Statistical Analysis Plan

A Prospective, Multi-Center, Non-Randomized, Safety and Efficacy Clinical Study of the LEGION™ Primary Knee System for Primary Total Knee Replacement in Subjects with Degenerative Knee Disease

Number: 10-4042
ST: 1113
Version: Final 1.0, 15-Feb-2021
Page: 10 of 18

Change from pre-operative to post-operative visits

Change from pre- to post-operative visit would be calculated as:

$$\text{Post - operative value}_{\text{visit } n} - \text{Pre - operative value}_{(\text{visit } 1)}, \text{ where } n = 3, 4, \dots$$

Knee Society Score (KSS) Endpoints

The Knee Society Score (KSS) comprises information on Objective Knee Indicators (range 0 to over 100 points), Patient Satisfaction (range 0-40), Patient Expectation (range 0-15), and Functional Activities (range 0-100). The KSS endpoints are derived from a series of questions that relate to everyday activities. More elaborate information for deriving the KSS endpoints are described in the publication by Scuderi et al (2012). However, an abbreviated description of the KSS endpoints used in the study is described in this SAP.

- *Objective Knee Score (Completed by Physician/Surgeon)*
- The objective score allows for more than 100 points in patients with greater than 125° of flexion and a stable painless knee as outlined below.
 - “Alignment” allows for a maximum of 25 points and is determined on a weight-bearing AP radiograph measuring the femoral-tibial (Anatomic) axis.

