 - “Instability” allows for a maximum of 25 points for a knee that is stable in the coronal and sagittal axis.
 - “Joint Motion” allows one point for each 5° of joint motion with a potential for greater than 25 points to be assigned for patients with greater than 125° of motion. There are deductions for flexion contracture and extension lag.
 - “Instability” has a maximum allowable point allocation of 25+.
 - “Symptoms” category contains two 10-level scales, ranging from “none” to “severe” for each patient to rate pain encountered when walking on level ground and on stairs/inclines. For this, a patient starts with 10 points on each scale for a painless knee with deductions of up to 10 points deductions as indicated by the patient’s

CONFIDENTIAL AND PROPRIETARY

This document contains information that is confidential and proprietary to Smith & Nephew PLC and Smith & Nephew, Inc. and is intended for use only by Smith+Nephew and its manufacturer. It shall not be reproduced or copied in whole or in part, nor shall the contents be disclosed by any means without prior written permission from Smith+Nephew, nor shall anyone make any use of it that is contrary to the expressed or implied wishes of Smith+Nephew.

Statistical Analysis Plan

A Prospective, Multi-Center, Non-Randomized, Safety and Efficacy Clinical Study of the LEGION™ Primary Knee System for Primary Total Knee Replacement in Subjects with Degenerative Knee Disease

Number: 10-4042
ST: 1113
Version: Final 1.0, 15-Feb-2021
Page: 11 of 18

response on each pain scale. There is an additional question regarding how "normal" the knee feels to the patient. The maximum allowable point is 25.

Patient Expectations and Satisfaction (Completed by Patient)

- "Patient Expectations" is a three-question fifteen-point scale that is collected pre-operatively and post-operatively. The pre-operative questions reflect a patient's opinion on the extent to which s/he expects that the operation will improve his/her knee pain, and the ability to perform activities of daily living and recreational activities.
- The post-operative patient expectations questions reflect the extent to which the outcome after the operation has met the patient's pre-operative expectations with respect to pain and function. "Patient Satisfaction" is a five-question 40-point scale that is collected preoperatively and at each follow-up visit.
- *Functional Score (Completed by Patient)*

CONFIDENTIAL AND PROPRIETARY

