This document contains information that is confidential and proprietary to Smith & Nephew PLC and Smith & Nephew, Inc. and is intended for use only by Smith+Nephew and its manufacturer. It shall not be reproduced or copied in whole or in part, nor shall the contents be disclosed by any means without prior written permission from Smith+Nephew, nor shall anyone make any use of it that is contrary to the expressed or implied wishes of Smith+Nephew.

Statistical Analysis Plan

A Prospective, Multi-Center, Non-Randomized, Safety and Efficacy Clinical Study of the LEGION™ Primary Knee System for Primary Total Knee Replacement in Subjects with Degenerative Knee Disease

Number: 10-4042
ST: 1113
Version: Final 1.0, 15-Feb-2021
Page: 12 of 18

- The functional score is composed of the four subgroups and has a maximum score of 100 as follows:
 - “Walking and Standing” has a maximum value of 30 points with deductions for the use of walking aids and supports.
 - “Standard Activities” has a maximum of 30 points and evaluates “standard” activities of daily living. Patients can also respond if they never participate in the activities. Patients who respond “I never do this” receive zero points for that activity.
 - “Advanced Activities” has a maximum of 25 points and evaluates function in performing more vigorous activities ranging from climbing a ladder or step-stool to running. Patients can also respond if they never participate in the activities. Patients who respond “I never do this” receive zero points for that activity.
 - “Discretionary Activities” has a maximum of 15 points and allows patients to select the three activities that they consider most important to them personally from a group of seventeen recreational and exercise activities. Patients who do not participate in any of the discretionary activities will have a functional knee score that is limited to 85 points. The discretionary activities do not need to be identical in the pre-operative and post-operative period.

Knee Osteoarthritis Outcome Score (KOOS)

Each item (question) that is used for scoring the KOOS is rated on a scale of 0 to 4 as follows:

- 0 = None; 1 = Mild; 2 = Moderate; 3 = Severe and; 4 = Extreme.

CONFIDENTIAL AND PROPRIETARY

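### SAP 7.3 fills missing KSS items with a plain average and defines neither domain nor item, so scores go out of range or are biased wherever item maxima differ

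*SAP*

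**What the plan says.** SAP 7.3 applies imputation to the KSS endpoints when under half of the responses in a domain are absent. The stated method is that "imputation with values equal to the average of all of the other items in the same domain would be used". The section attributes the rule to the 2012 KSS User Manual. It does not say what counts as a domain or an item, and it gives no rescaling and no cap.

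SAP 7.4 describes the scores to which the rule applies:

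- **Objective.** The range runs from 0 to over 100. One of its categories, Symptoms, has two pain scales, on which "a patient starts with 10 points on each scale for a painless knee", and a further question on how normal the knee feels. For the category, "The maximum allowable point is 25".
- **Functional.** There are four subgroups. The walking subgroup and the standard-activities subgroup are each worth up to 30 points. The advanced subgroup "has a maximum of 25 points and evaluates function in performing more vigorous activities". The discretionary subgroup carries 15 points from three chosen activities.
- **Satisfaction and Expectations.** Satisfaction has five questions for 40 points, and Expectations has three for 15. The points per question are not stated.

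SAP 7.11 summarises all KSS scores descriptively by visit. It also summarises change from preoperative to each postoperative visit, except for KSS expectation.

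**The concern.** Replacing a missing item with the mean of the others assumes that all items are on the same scale. The KOOS items in SAP 7.4 are (each 0 to 4), so averaging is sound there. Some KSS items are not. Where a low-maximum item is missing, the average of higher-maximum items can exceed anything the missing item could score. Where a high-maximum item is missing, the fill-in is too low. The size and direction of the error therefore depend on which question was left blank.

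The error need not cancel in change scores, because it grows with the level of the observed items. The study has no concurrent arm that would share the bias. SAP section 2 makes the SAP the guideline for programming the tables, so the rule is likely to be coded as written. A range check on the Objective total would not reliably catch an inflated value, because that total may properly exceed 100.

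**Working it through.** **Inputs.** The rule and the under-50% condition are from SAP 7.3. The maxima are from SAP 7.4:

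- Symptoms: 10, 10 and, by subtraction, 25 − 10 − 10 = 5.
- Functional subgroups: 30, 30, 25, 15.
- Objective: four categories (Alignment, Instability, Joint Motion, Symptoms) at 25 each, where Joint Motion may exceed 25. SAP 7.4 lists Instability twice; I count it once.

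**The plan's own figures.** 30 + 30 + 25 + 15 = 100, and 100 − 15 = 85 for a subject with no discretionary activity. Both match SAP 7.4.

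**Formulas.**

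- Rule as written: missing item = sum of observed points / number of observed items.
- Proportional rule: missing item = item maximum × (sum of observed points / sum of observed item maxima).

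**Results with every observed item at full score.** One missing of 3, 4 or 6 items is 33%, 25% or 17%, so imputation applies in each case.

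| Unit and missing item | Fill-in as written | Total as written | Proportional total |
|---|---|---|---|
| Symptoms, third item (max 5) | (10 + 10)/2 = 10 | 30 | 25 |
| Symptoms, one pain item (max 10) | (10 + 5)/2 = 7.5 | 22.5 | 25 |
| Functional subgroups, Discretionary (max 15) | (30 + 30 + 25)/3 = 28.3 | 113.3 | 100 |
| Functional subgroups, Walking or Standard (max 30) | (30 + 25 + 15)/3 = 23.3 | 93.3 | 100 |
| Functional subgroups, Advanced (max 25) | (30 + 30 + 15)/3 = 25 | 100 | 100 |
| Objective, four categories (max 25 each) | 25 | 100 | 100 |
| Objective, single items (25, 25, 25, 10, 10, 5), third Symptoms item | 95/5 = 19 | 114 | 100 |

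The last row assumes that Alignment, Instability and Joint Motion each count as one 25-point item.

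**When values leave the range.**

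- Symptoms, third item missing, pain items summing to S: the fill-in S/2 exceeds 5 once S is above 10. The total 1.5 × S exceeds 25 once S is above 16.7.
- Functional, Discretionary missing, other subgroups summing to T: the total T + T/3 exceeds 100 once T is above 75 of 85.

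Below these points the total stays in range but can still be biased. At 80% of maximum throughout, Symptoms with the third item missing gives 16 + 8 = 24 instead of 20. Functional with Discretionary missing gives 68 + 22.7 = 90.7 instead of 80.

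**Change scores.** With the third Symptoms item missing, the excess over the proportional fill is S/2 − 5S/20 = S/4. As an illustration with assumed values, pain items of 3 and 3 before surgery give an excess of 6/4 = 1.5, and 9 and 9 afterwards give 18/4 = 4.5. If the item is missing at both visits, improvement is overstated by 4.5 − 1.5 = 3 points on a 25-point category.

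**Where nothing changes.** Assuming equal weights, Satisfaction (40/5 = 8 per question), Expectations (15/3 = 5) and Discretionary (15/3 = 5 per activity) give the same result under both rules.

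**The case against.** The strongest reply is that the worked cases depend on a definition the SAP does not give. Symptoms is a category within Objective. If Objective is the domain and its four 25-point categories are the items, the plain average does no harm. The SAP also calls its KSS description abbreviated and attributes the rule to a manual that may restrict it or rescale. The effect is small as well: +5 or −2.5 points in the two Symptoms cases, on a component that runs to over 100, in descriptive summaries of a secondary endpoint.

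Much of this stands, and it sets the limits of the point. It does not remove it. SAP 7.3 counts missing responses, and SAP 7.4 says the KSS is built from a series of questions, so the question is the natural unit. On that unit, a painless knee gets too high a value for the 5-point item whether the domain is Symptoms (10) or, on the single-item listing, the whole Objective score (19). The manual cannot be checked here, and citing it does not supply a rescaling that the SAP text lacks.

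A reader might infer that all KSS scores are distorted, or that the manual's method is wrong. The documents support neither. Several scores are unaffected under equal weighting, and the manual's wording is not reproduced.

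**Conclusion.** The point holds in a limited form. As written, SAP 7.3 gives out-of-range or biased values where item maxima differ. This affects Symptoms when single questions are imputed, and Functional if its subgroups are the items. Item maxima within Walking and Standing, Standard Activities and Advanced Activities are not given, so imputation at question level there cannot be assessed.

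The conclusion rests on reading the average literally, on deriving 5 points for the third Symptoms item by subtraction, and on equal weighting for the scores called unaffected. The share of records with a missing KSS item is not given, so the effect on any reported mean cannot be stated.

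It would be wrong to conclude that the study's main result is at risk. The primary endpoint is implant survivorship, which does not use the KSS. SAP 7.11 specifies no KSS test. The matter is worth correcting because the SAP's own maxima show the rule producing scores that cannot occur, and the correction is cheap.

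**What to change.** In SAP 7.3:

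1. Define domain and item for each KSS score, stating whether Symptoms and the Functional subgroups are domains, items or neither.
2. Keep the under-50% condition and impute as item maximum × (sum of observed points / sum of observed item maxima). Alternatively, limit the plain average to sets of equally weighted items and say how the others are handled.
3. Apply any cap to the imputed item's own maximum. Do not cap the domain, Objective or Joint Motion total, because SAP 7.4 lets Objective exceed 100 and Joint Motion exceed 25. If Joint Motion is among the observed items, state the nominal maximum used for it in the formula.
4. Check the wording against the cited manual and record any departure from it in 7.3. SAP 7.15 covers changes from the protocol, and the protocol specifies no KSS imputation.

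The cost is a few sentences in 7.3 and a matching change in the derivation program. The downside is that some scores may differ slightly from those under the manual's literal wording, which is why any departure should be stated.
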